Where was questionnaire completed: home clinic another centre

Comments: _____

Date Completed: ____ - ____ - ____
 yyyy mmm dd

*PLEASE ENSURE THIS PAGE IS FOLDED BACK BEFORE HANDING
TO THE PATIENT FOR QUESTIONNAIRE COMPLETION.*

CCTG use only

Logged: _____

Study Coord: _____

Res Assoc: _____

Data Ent'd: _____

Verif: _____

____ - ____ - ____

____ - ____ - ____

____ - ____ - ____

**FSDS-R QUESTIONNAIRE - FEMALE SEXUAL DISTRESS SCALE-Revised
CCTG CX.5**

INSTRUCTIONS

Below is a list of feelings and problems that women sometimes have concerning their sexuality. Please read each item carefully, and circle the number that best describes **HOW OFTEN THAT PROBLEM HAS BOTHERED YOU OR CAUSED YOU DISTRESS DURING THE PAST 30 DAYS INCLUDING TODAY***. Circle only one number for each item, and take care not to skip any items. If you change your mind, erase your first circle carefully. Read the example before beginning, and if you have any questions please ask about them.

*** AT BASELINE ONLY:** If there has been a period of no sexual activity (whether with a partner or on your own) because of a recent medical procedure, please complete this with the most recent 4-week period that did include sexual activity.

Example: How often did you feel: Personal responsibility for your sexual problems.

NEVER RARELY OCCASIONALLY FREQUENTLY ALWAYS
 0 1 2 3 4

HOW OFTEN DID YOU FEEL:	NEVER	RARELY	OCCASIONALLY	FREQUENTLY	ALWAYS
1. Distressed about your sex life	0	1	2	3	4
2. Unhappy about your sexual relationship	0	1	2	3	4
3. Guilty about sexual difficulties	0	1	2	3	4
4. Frustrated by your sexual problems	0	1	2	3	4
5. Stressed about sex	0	1	2	3	4
6. Inferior because of sexual problems	0	1	2	3	4
7. Worried about sex	0	1	2	3	4
8. Sexually inadequate	0	1	2	3	4
9. Regrets about your sexuality	0	1	2	3	4
10. Embarrassed about sexual problems	0	1	2	3	4
11. Dissatisfied with your sex life	0	1	2	3	4
12. Angry about your sex life	0	1	2	3	4
13. Bothered by low sexual desire	0	1	2	3	4

FSFI QUESTIONNAIRE - CCTG CX.5
Female Sexual Function Index (FSFI) ©

These questions ask about your sexual feelings and responses during the past 4 weeks. Please answer the following questions as honestly and clearly as possible using the scale to the right. Your responses will be kept completely confidential. If you choose not to answer a particular question, please proceed to the next question.

In answering these questions, the following definitions apply:

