Sexual activity can include caressing, foreplay, masturbation, and vaginal intercourse.

Sexual intercourse is defined as penile penetration (entry) of the vagina.

Sexual stimulation includes situations like foreplay with a partner, self-stimulation (masturbation), or sexual fantasy.

Sexual desire or interest is a feeling that includes wanting to have a sexual experience, feeling receptive to a partner's sexual initiation, and thinking or fantasizing about having sex.

Sexual arousal is a feeling that includes both physical and mental aspects of sexual excitement. It may include feelings of warmth or tingling in the genitals, lubrication (wetness), or muscle contractions.

Circle only one item per question.

Question	Response options (please circle)
1. Over the past 4 weeks, how satisfied have you been with your overall sexual life?	5 = Very satisfied 4 = Moderately satisfied 3 = About equally satisfied & dissatisfied 2 = Moderately dissatisfied 1 = Very dissatisfied
2. Over the past 4 weeks, how often did you feel sexual desire or interest?	5 = Almost always or always 4 = Most times (more than ½ the time) 3 = Sometimes (about ½ the time) 2 = A few times (less than ½ the time) 1 = Almost never or never
3. Over the past 4 weeks, how would you rate your level (degree) of sexual desire or interest?	5 = Very high 4 = High 3 = Moderate 2 = Low 1 = Very low or none at all

Question

Response options (please circle)

- | | |
|---|---|
| 4. Over the past 4 weeks, did you engage in sexual activity of any kind with a partner and/or by yourself (masturbation)? | 0 = No sexual activity (neither with a partner nor by myself) |
| | 1 = Sexual activity with a partner only |
| | 1 = Sexual activity by myself only |
| | 1 = Sexual activity both with a partner and by myself |

If you selected “0 = No sexual activity (neither with a partner nor by myself)”, please skip remaining questions on this questionnaire. If you selected any other response, please continue.

- | | |
|--|--|
| 5. Over the past 4 weeks, how often did you feel sexually aroused (“turned on”) during sexual activity or intercourse? | X = No sexual activity |
| | 5 = Almost always or always |
| | 4 = Most times (more than ½ the time) |
| | 3 = Sometimes (about ½ the time) |
| | 2 = A few times (less than ½ the time) |
| | 1 = Almost never or never |

- | | |
|--|-----------------------------|

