7.8.1.4 FSDS-R

The FSDS-R is a 13-item unidimensional measure of sexual-related distress.

- Total Score $Q1+...+Q13$

For all the above PRO questionnaire, missing items in a multiitem scale will be handled by the following methods: Values will be imputed for missing items by “assuming that the missing items have values equal to the average of those items which are present” for the total score in which at least half the items are completed. The total score will be treated as missing if less than half of the items are completed.

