7.8.4 Analyses of PRO

7.8.4.1 Baseline and Change Score Analysis

Descriptive statistics for EORTC QOL-C30, CX24, FSDI and FSDS-R scores (mean, standard deviation) will be presented for each scale and summary scale at baseline for each treatment group (**Table 43**). The change scores from baseline will be generated at each time of post-baseline evaluation and compared between two arms by Wilcoxon test (**Table 44**).

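### A woman with no sexual activity in the four weeks before baseline has no baseline FSFI total, and because the SAP analyses only change from baseline, all her follow-up FSFI totals are lost too

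*Protocol*

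**What the plan says.** **FSDS-R (Protocol, Appendix VI).** The standard question is "HOW OFTEN THAT PROBLEM HAS BOTHERED YOU OR CAUSED YOU DISTRESS DURING THE PAST 30 DAYS INCLUDING TODAY". At baseline only, a woman whose inactivity is due to a recent procedure is instructed: "please complete this with the most recent 4-week period that did include sexual activity".

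**FSFI (Protocol, Appendix VI).** "These questions ask about your sexual feelings and responses during the past 4 weeks". No baseline exception is printed. Items 1 to 3 cover overall satisfaction and the two desire questions (for example "Over the past 4 weeks, how often did you feel sexual desire or interest"). Item 4 asks about activity of any kind, alone or with a partner, and a woman who reports none is told: "please skip remaining questions on this questionnaire".

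**Missing items (SAP 7.8.1.4, applied to all the questionnaires).** "The total score will be treated as missing if less than half of the items are completed".

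**Analysis.** SAP 7.8.4.1: "The change scores from baseline will be generated at each time of post-baseline evaluation and compared between two arms by Wilcoxon test". SAP 7.8.4.2 fits a linear mixed model, also to change scores. No planned arm comparison uses post-baseline scores that have not been differenced from baseline.

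**Compliance (SAP 7.8.3).** A questionnaire counts as filled out if one question is answered.

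**Role of the scales.** Protocol 2.5.3 makes FSDS-R change Hypothesis 2 and FSFI-total change Hypothesis 3. Protocol 2.5.4 ranks distress first and function second within sexual health. Neither Protocol 14.6 nor SAP 7.8 mentions the FSDS-R exception or a value for skipped FSFI items, and the form has no dedicated field for which recall period was used.

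**The concern.** The FSDS-R instruction shows that the sponsor foresaw women being inactive at baseline because of the diagnostic procedure. The provision was made on one scale only. On the other, a state that may be temporary and precedes randomization removes the baseline total. The change-score analysis then removes every later total from the same woman. The measure at stake is the one in Hypothesis 3, which has the largest sample size requirement of the three patient-reported hypotheses. The loss would not appear in the compliance table, because her form counts as received.

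A second, smaller matter concerns the FSDS-R. For women who used the exception, baseline refers to an earlier period selected for activity, while follow-up refers to the most recent 30 days without that selection. Their within-arm change combines surgery with the change of window, and without a recorded flag the two cannot be separated.

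**Working it through.** **1. The plan's own sample sizes.** Protocol 14.6 gives totals of 120, 130 and 560 for differences of 7, 5 and 5 points with SDs of 13.5, 10 and 21, at 80% power and two-sided 0.05. (The text there prints FSDS-R twice; Table 1 in Protocol 2.5.4 shows that 21 belongs to the FSFI total.) The normal-approximation formula is

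n per arm = 2 × (1.960 + 0.842)² × (SD/δ)², with total = 2n.

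- QLQ-CX24 symptom scale: 2 × 7.849 × (13.5/7)² = 58.4, so 59 per arm, total 118 (t-test version 120; stated 120).
- FSDS-R: 2 × 7.849 × (10/5)² = 62.8, so 63 per arm, total 126 (t-test version 128; stated 130).
- FSFI total: 2 × 7.849 × (21/5)² = 276.9, so 277 per arm, total 554 (t-test version 556; stated 560).

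The stated figures reproduce to rounding.

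**2. What an inactive woman leaves on the FSFI form.** The printed form has 20 items, of which item 4 is the activity screen and 19 are scored. With no activity she answers items 1 to 3.

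- Scored items answered: 3/19 = 16%. If the SAP's Q1 to Q19 numbering is applied literally to the 20-item form, it is 4/19 = 21%. Both are below half, so the total is missing.
- By item content: Desire 2 of 2 (scoreable); Satisfaction 1 of 3 (missing); Arousal, Lubrication, Orgasm and Pain 0 items (missing). Five of the six domains are lost.

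**3. Carry-forward into the analysis.** Change at visit t is score(t) minus baseline. With baseline missing, change is undefined at 3, 6, 12, 24 and 36 months, whatever she reports then.

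**4. Size, as a function of the unknown share f with no baseline total.** The number left is 700 × (1 − f). Power for 5 points with SD 21 is Φ(5 / (21 × √(2/n)) − 1.960), with n = 350 × (1 − f) per arm.

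| f (assumed) | women left | power |
|---|---|---|
| 0% | 700 | 88% |
| 10% | 630 | 85% |
| 20% | 560 | 80% |
| 30% | 490 | 75% |
| 43.3% | 397 | 66% |

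The stated 560 is reached exactly at f = 1 − 560/700 = 20%. On the 750 randomized patients given in SAP 2.1, the corresponding share is 1 − 560/750 = 25%. These figures are upper limits: the sexual health component is optional (Protocol 6.0, note 6), the questionnaires depend on language (Protocol 5.1.7), and no loss at follow-up is counted.

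**5. Recall windows side by side.** FSFI: four weeks at baseline and four weeks at follow-up. FSDS-R: 30 days at follow-up; at baseline 30 days, or an earlier active four-week period for women who used the exception. A window mismatch therefore arises only in FSDS-R change, and only for those women.

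**The case against.** The strongest reply is that this is a secondary, optional component; that baseline forms precede randomization, so the loss cannot favour an arm; that the operational hypotheses in Protocol 14.6 are between-arm; and that the FSDS-R exception looks like a deliberate choice of a pre-procedure reference. All of that stands. It limits the consequence, but it does not give a reason to discard follow-up scores that have been collected.

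Several stronger readings are tempting and should be set aside:

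- *That women abstaining after a cone have no FSFI baseline at all.* Desire remains scoreable. The skip applies only to no activity of any kind over the full four weeks, and the form's definition of activity is wider than intercourse. The documents do not say how soon after the procedure baseline usually falls; they require only that it be within 6 weeks before randomization.
- *That FSFI change also compares different windows.* It does not; the FSFI period is the same throughout.
- *That the rise in distress expected in both arms is built in by the window.* The documents do not say whether distress is higher or lower in an active month, so the direction is unknown.
- *That about 43% would be lost.* The 43.3% in Protocol 2.5.2 describes long-term survivors whose leading reasons for inactivity were lack of a partner and lack of desire. It serves here only as a scenario.
- *That the arm comparison is biased.* Nothing in the documents supports this.

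**Conclusion.** The point holds as a loss of information. Under the printed skip rule, the half-of-items rule and a change-score-only analysis, any woman inactive for the whole four weeks before baseline drops out of the FSFI-total comparison at every visit, and the compliance table does not reveal it. The plan can absorb a 20% loss from 700 before falling below its own 560, if nothing else is lost. At 30% power is about 75%, and at 43.3% about 66%. These shares are assumptions; the true one is not in the documents.

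The cost is precision and representativeness: the FSFI result would describe only women who were sexually active just before baseline. For the FSDS-R, the between-arm comparison is not put in doubt, but within-arm change among women who used the exception cannot be attributed to surgery. The point merits a change to the SAP because the remedy is cheap.

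**What to change.** In SAP 7.8.4.2, analyse the FSFI total and domains with the scores themselves as outcomes: baseline as one of the repeated measurements, visit as a categorical factor, and a common baseline mean for the two arms, which randomization justifies. Women without a baseline total then keep their follow-up scores. Keep the Wilcoxon change-score comparison in 7.8.4.1 as supportive.

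The downside is a missing-at-random assumption for the absent baselines, which the SAP should state. It is no stronger than what is already implied when the change-score result is read as applying to all women. The model does not restore totals missing at follow-up because a woman is inactive then, and it does not address the FSDS-R window.

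Add two reporting items. Give, by arm, the number of women with a form received but no baseline FSFI total. State that FSDS-R baseline may refer to an earlier period for some women, and that within-arm FSDS-R change is not interpreted as an effect of surgery.

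Copying the FSDS-R exception to the FSFI form is not recommended. Accrual closed in November 2019 (SAP 2.1), so it could recover nothing, and it would create in the FSFI the window mismatch now confined to the FSDS-R.

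The cost is SAP wording and one model specification, with no new data.

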APPENDIX VII - HEALTH UTILITIES ASSESSMENT

Introduction

Note: Health Utilities Assessment applies to Canadian and UK centres only. Patients from these centres should complete the quality of life assessment before the health utilities assessment.

The assessment of overall health benefits is complicated by the need for a measure that can combine various benefits, such as overall survival, progression free survival, and quality of life into a single measure of benefit. Patients may value particular benefits differently. There is no obvious way to add together independently collected benefits for an individual or for a trial to yield a measure of overall benefit. Health utilities are a measure of how people value particular health outcomes. They provide a common denominator that can be combined with survival to form a measure of overall health benefits.

Such a measure of overall health benefit can then be used as part of a health economic analysis. Health economic analyses assess the benefits and costs of an intervention, for consideration whether the intervention may be worth its "costs" -- including financial, toxicity, and social costs.

The collection of information about health utilities is becoming more common in clinical protocols. In clinical trials, health utilities are most often collected using a patient self-reported questionnaire (similar to the collection of quality of life data).

Health utility and quality of life assessments provide different but complementary information.

- Health utility is a measure of preference for a given health state that acknowledges the risk and uncertainty of outcomes in choices patients face and in clinical decision-making.
- They can be used as a weighting factor to adjust survival by quality of life.
- Depending on whether a disease-specific or generic quality of life instrument is used, often only utility assessments may be able to compare patient groups with different diseases.
- Only utilities provide a single meaningful measure that can be incorporated in health policy and health economic analyses.

Health utilities data can be used in a variety of ways:

- to try and achieve the best possible outcome for patients and populations
- to evaluate the extent of change in health benefits of an individual, group, or population across time
- to evaluate new treatments, technologies, and patient management strategies
- to support approval of new drug applications or patient management strategies
- to try to provide the best value for health care dollars within and across diseases and health
- to compare costs and benefits of various financial and organizational aspects of health care services

In the future, approval of new therapies or patient management strategies will most likely be based on a combination of health benefit and cost data. This may be formally done using health utilities as part of a health economic analysis.

Instructions for Administration of a Health Utilities Questionnaire

The instructions below are intended as a guide for the administration of the Health Utilities Questionnaire

1. Preamble

Health utilities data are collected for research purposes, and will not be used for the patient's individual medical care. The assessment is in the form of a self-report questionnaire. Therefore, it must be completed by the patient only, without translation, coaching or suggestions as to the "correct" answer by relatives or health care personnel.

The usual scheduled times to obtain the questionnaires are as follows:

- pre-randomization or pre-registration (baseline)
- during treatment
- during follow-up

The information provided by the patient in the completed questionnaire is confidential and should not be discussed with or shown to anyone who is NOT mentioned in the consent form signed by the patient.

If a particular question has not been answered, please document the reason(s) in the appropriate space on the questionnaire. If the whole questionnaire has not been completed, please document the reason(s) on the appropriate case report forms.

2. Pre-treatment Assessment

It should be explained to the patient that the purpose of the questionnaire is to assess the impact of treatment on different areas of the patient's life, e.g. psychological distress, social disruption, symptoms, side-effects, *et cetera*.

The Clinical Research Associate (CRA) should collect the questionnaire as soon as it has been completed, check to see that each question has been answered and gently remind the patient to answer any inadvertently omitted questions. If a patient states that she prefers not to answer some questions and gives a reason(s), the reason(s) should be noted on the questionnaire. If a specific reason is not given, this also should be noted on the questionnaire.

3. Assessments During Treatment

The health utilities questionnaire should be given to the patient before being seen by the doctor, and prior to treatment on the day of treatment, as required by the schedule in the protocol. If the patient does not have a doctor visit scheduled, or if it was not possible for the patient to complete the questionnaire before being seen by the doctor, she should still complete the questionnaire prior to treatment.

4. Assessments During Follow-up

The health utilities questionnaire should be given to the patient before being seen by the doctor, at every follow-up visit, as required by the protocol schedule in section 9.1 or until deterioration to ECOG PS 4 or hospitalization for end-of-life-care.

To minimize missing health utilities data, if the patient is no longer attending clinic during the scheduled follow-up period, the patient should be contacted by phone to ask him/her to complete the questionnaire and mail it to the clinic. To facilitate this, ensure that after randomization all patients are provided with 2 blank questionnaires and 2 clinic-addressed stamped envelopes. When the questionnaire is returned, the date on which the questionnaire was completed should be noted on the appropriate case report form, as well as where and why the patient completed the questionnaire outside of the clinic. If the patient has deterioration to ECOG PS 4 or hospitalization for end of life care they need not be contacted for questionnaire completion.

A patient may, on occasion, be reluctant to complete the questionnaire because they feel unwell. In that case, you may express sympathy that things are below par, but state that this is exactly the information we require if we are to understand more about how overall health is affected. You may also remind them that it takes only a few minutes to complete.

It defeats the whole purpose of the assessment if it is delayed until the patient feels better!

5. What If...

The patient should complete the questionnaires at the clinic. The exception is that the design of some trials may require the patient to take the questionnaire home with them after leaving the clinic, and complete it on the specific day, because a return visit to the clinic is not scheduled.

There may be circumstances when the patient does not complete the questionnaire as required in the clinic. Four situations are described below. In these cases, it is beneficial if health economics data can still be collected.

- A. The patient leaves the clinic before the questionnaire could be administered, or someone forgets to give the questionnaire to the patient.

Contact the patient by phone informing him or her that the questionnaire was not completed. Ask the patient if she is willing to complete one:

If yes, mail a blank questionnaire to the patient, and make arrangements for return of the questionnaire in a timely fashion. Record the date it was mailed and the date received on the questionnaire.

If this is not feasible, then ask the patient if she is willing to complete a questionnaire over the phone. If the patient agrees, read out questions 1-5 and range of possibilities, and record the answers. The visual analogue scale should not be completed in this case. Make a note on the questionnaire that the questionnaire was completed over the phone.

If no, note the reason why the questionnaire was not completed on the appropriate case report form.

- B. The patient goes on an extended vacation for several months and won't attend the clinic for regular visit(s).

Ensure that the patient has a supply of questionnaires, with instructions about when to complete them, and how to return them. If it is known beforehand, give the patient blank questionnaires at the last clinic visit; if the extended absence is not known in advance, mail the blank questionnaires to the patient. Written instructions may help ensure that the patient stays on schedule as much as possible.

- C. The patient does not want to complete the questionnaire in clinic.

Should the patient not wish to answer the questionnaire in the clinic but insists on taking it home, and failing to comply with the patient's wishes is likely to result in the questionnaire not being completed at all, then the patient may take the questionnaire home with instructions that it is to be completed the same day. When the questionnaire is returned, the date on which the questionnaire was completed should be noted and a comment made on the questionnaire as to why the patient took it away from the clinic before completion.

D. The patient is no longer attending clinic during the scheduled follow-up period.

Should the patient no longer be attending clinic, she should be contacted by phone to ask her to complete the questionnaire and mail it to the clinic. To facilitate this, ensure that after randomization all patients are provided with 2 blank questionnaires and 2 clinic-addressed stamped envelopes. When the questionnaire is returned, the date on which the questionnaire was received should be recorded on the questionnaire. The date on which the questionnaire was completed should be noted on the appropriate case report form, as well as where and why the patient completed the questionnaire outside of the clinic. If the patient has deterioration to ECOG PS 4 or hospitalization for end of life care they need not be contacted for questionnaire completion.

6. Waiving the Health Utilities Component

The only time that we will not require a patient to complete the health utilities questionnaires is if she is not literate in either English or French. In other words, if the assistance of a translator is required to comprehend the questions and reply, the questionnaires should not be completed. Translation of the questions is not acceptable. Please indicate on questionnaire.

7. Unwillingness to Complete Health Utilities Questionnaire

If a patient speaks and reads English or French, but does not wish to complete the questionnaires then she is NOT eligible and should NOT be put on study.

8. Inability to Complete Health Utilities Questionnaire (for reason other than illiteracy in English or French)

An eligible patient may be willing but physically unable to complete the questionnaires, because of blindness, paralysis, etc. If the patient is completing the HUI3 assessment in the clinic, the questionnaire should be read to them and the answers recorded by a health care professional (e.g. preferably the clinical research associate assigned to the trial, but another clinic nurse, a doctor or social worker who is familiar with the instructions for administering the questionnaires would be acceptable). If the patient is completing the questionnaire at home, and a telephone interview by the clinical research associate is not possible, then a spouse or friend may read the questions to the patient and record the answers. However, this method should be a last resort, and the spouse or friend should be instructed to not coach or suggest answers to the patient. Whichever method is used, it should be recorded on the questionnaire.

If these special arrangements are not possible or feasible, then the patient would not be required to complete the questionnaires, and this should be reported on the appropriate case report form.

Health Utilities Questionnaire – **ENGLISH**
CCTG Trial: CX.5

This page to be completed by the Clinical Research Associate

Patient Information

CCTG Patient Serial No: _____

Patient Initials: _____
(first-middle-last)

Institution: _____

Investigator: _____

Scheduled time to obtain quality of life assessment: please check (3)

Prior to randomization

At the time of first recurrence

After surgery prior to recurrence:

3 months

6 months

9 months

12 months

16 months

20 months

24 months

30 months

36 months

Other _____ (specify)

Were ALL questions answered? ___ Yes ___ No If no, reason: _____

Was assistance required? ___ Yes ___ No If yes, reason: _____

Where was questionnaire completed: home clinic another centre

Comments: _____

Date Completed: ____ - ____ - ____
 yyyy mmm dd

*PLEASE ENSURE THIS PAGE IS FOLDED BACK BEFORE HANDING
TO THE PATIENT FOR QUESTIONNAIRE COMPLETION.*

CCTG use only

Logged: _____
_____ - _____ - _____

Study Coord: _____
_____ - _____ - _____

Res Assoc: _____
_____ - _____ - _____

Data Ent'd: _____

Verif: _____

Health Utilities Index Mark 3 (HUI3) Questionnaire

CCTG: CX.5

This questionnaire contains a set of questions which ask about various aspects of your health. When answering these questions please think about your health and your ability to do things on a day-to-day basis, during the past week. For each question, please select one answer that best describes your level of ability or disability during the past week. Please answer all the questions yourself by circling the letter (a, b, c, ...) beside the answer that best applies to you. Choose the best single response that applies to you. There are no right or wrong answers; what we want is your opinion about your abilities and feelings. To define the past week period, please think about what the date was 7 days ago and recall the major events that you have experienced during this period. Please focus your answers on your abilities, disabilities and how you have felt during the past week.

You may feel that some of these questions do not apply to you, but it is important that we ask the same questions of everyone. Also, a few questions are similar; please excuse the apparent overlap and answer each question independently.

The information that you provide is for research purposes and will remain strictly confidential. The individuals (e.g. doctors, nurses, etc.) directly involved in your care will not usually see your responses to these questions -- if you wish them to know this information, please bring it to their attention.

-
1. Which one of the following best describes your ability, during the past week, to see well enough to read ordinary newsprint?
 - a. Able to see well enough without glasses or contact lenses.
 - b. Able to see well enough with glasses or contact lenses.
 - c. Unable to see well enough even with glasses or contact lenses.
 - d. Unable to see at all.

 2. Which one of the following best describes your ability, during the past week, to see well enough to recognize a friend on the other side of the street?
 - a. Able to see well enough without glasses or contact lenses.
 - b. Able to see well enough with glasses or contact lenses.
 - c. Unable to see well enough even with glasses or contact lenses.
 - d. Unable to see at all.

3. Which one of the following best describes your ability, during the past week, to hear what was said in a group conversation with at least three other people?
- a. Able to hear what was said without a hearing aid.
 - b. Able to hear what was said with a hearing aid.
 - c. Unable to hear what was said even with a hearing aid.
 - d. Unable to hear what was said, but did not wear a hearing aid.
 - e. Unable to hear at all.
4. Which one of the following best describes your ability, during the past week, to hear what was said in a conversation with one other person in a quiet room?
- a. Able to hear what was said without a hearing aid.
 - b. Able to hear what was said with a hearing aid.
 - c. Unable to hear what was said even with a hearing aid.
 - d. Unable to hear what was said, but did not wear a hearing aid.
 - e. Unable to hear at all.
5. Which one of the following best describes your ability, during the past week, to be understood when speaking your own language with people who do not know you?
- a. Able to be understood completely.
 - b. Able to be understood partially.
 - c. Unable to be understood.
 - d. Unable to speak at all.

6. Which one of the following best describes your ability, during the past week, to be understood when speaking with people who know you well?
- Able to be understood completely.
 - Able to be understood partially.
 - Unable to be understood.
 - Unable to speak at all.
7. Which one of the following best describes how you have been feeling during the past week?
- Happy and interested in life.
 - Somewhat happy.
 - Somewhat unhappy.
 - Very unhappy.
 - So unhappy that life was not worthwhile.
8. Which one of the following best describes the pain and discomfort you have experienced during the past week?
- Free of pain and discomfort.
 - Mild to moderate pain or discomfort that prevented no activities.
 - Moderate pain or discomfort that prevented some activities.
 - Moderate to severe pain or discomfort that prevented some activities.
 - Severe pain or discomfort that prevented most activities.

9. Which one of the following best describes your ability, during the past week, to walk? Note: Walking equipment refers to mechanical supports such as braces, a cane, crutches or a walker.
- a. Able to walk around the neighbourhood without difficulty, and without walking equipment.
 - b. Able to walk around the neighbourhood with difficulty; but did not require walking equipment or the help of another person.
 - c. Able to walk around the neighbourhood with walking equipment, but without the help of another person.
 - d. Able to walk only short distances with walking equipment, and required a wheelchair to get around the neighbourhood.
 - e. Unable to walk alone, even with walking equipment. Able to walk short distances with the help of another person, and required a wheelchair to get around the neighbourhood.
 - f. Unable to walk at all.
10. Which one of the following best describes your ability, during the past week, to use your hands and fingers? Note: Special tools refers to hooks for buttoning clothes, gripping devices for opening jars or lifting small items, and other devices to compensate for limitations of hands or fingers.
- a. Full use of two hands and ten fingers.
 - b. Limitations in the use of hands or fingers, but did not require special tools or the help of another person.
 - c. Limitations in the use of hands or fingers, independent with use of special tools (did not require the help of another person).
 - d. Limitations in the use of hands or fingers, required the help of another person for some tasks (not independent even with use of special tools).
 - e. Limitations in the use of hands or fingers, required the help of another person for most tasks (not independent even with use of special tools).
 - f. Limitations in the use of hands or fingers, required the help of another person for all tasks (not independent even with use of special tools).

11. Which one of the following best describes your ability, during the past week, to remember things?
- a. Able to remember most things.
 - b. Somewhat forgetful.
 - c. Very forgetful.
 - d. Unable to remember anything at all.
12. Which one of the following best describes your ability, during the past week, to think and solve day to day problems?
- a. Able to think clearly and solve day to day problems.
 - b. Had a little difficulty when trying to think and solve day to day problems.
 - c. Had some difficulty when trying to think and solve day to day problems.
 - d. Had great difficulty when trying to think and solve day to day problems.
 - e. Unable to think or solve day to day problems.
13. Which one of the following best describes your ability, during the past week, to perform basic activities?
- a. Eat, bathe, dress and use the toilet normally.
 - b. Eat, bathe, dress or use the toilet independently with difficulty.
 - c. Required mechanical equipment to eat, bathe, dress or use the toilet independently.
 - d. Required the help of another person to eat, bathe, dress or use the toilet.

14. Which one of the following best describes how you have been feeling during the past week?
- a. Generally happy and free from worry.
 - b. Occasionally fretful, angry, irritable, anxious or depressed.
 - c. Often fretful, angry, irritable, anxious or depressed.
 - d. Almost always fretful, angry, irritable, anxious or depressed.
 - e. Extremely fretful, angry, irritable, anxious or depressed; to the point of needing professional help.
15. Which one of the following best describes the pain or discomfort you have experienced during the past week?
- a. Free of pain and discomfort.
 - b. Occasional pain or discomfort. Discomfort relieved by non-prescription drugs or self-control activity without disruption of normal activities.
 - c. Frequent pain or discomfort. Discomfort relieved by oral medicines with occasional disruption of normal activities.
 - d. Frequent pain or discomfort; frequent disruption of normal activities. Discomfort required prescription narcotics for relief.
 - e. Severe pain or discomfort. Pain not relieved by drugs and constantly disrupted normal activities.
16. Overall, how would you rate your health during the past week?
- a. Excellent.
 - b. Very good.
 - c. Good.
 - d. Fair.
 - e. Poor.

17. How did you complete the questionnaire? Please select the one answer that best describes your situation.
- a. By myself, without any help from anyone else.
 - b. By myself, except someone else circled the answers on the questionnaire form for me.
 - c. With the help of someone else.
 - d. This questionnaire was completed by a family member, without help from the subject or patient.
 - e. This questionnaire was completed by a nurse or other health professional, without help from the subject or patient.
Please specify type of health professional: _____
 - f. This questionnaire was completed by another person, without help from the subject or patient.
Please specify relationship to subject or patient: _____

EQ-5D Questionnaire

CCTG: CX.5

By placing a tick in one box in each group below, please indicate which statements best describe your own health state today.

1. **Mobility**

- a. I have no problems in walking about
- b. I have some problems in walking about
- c. I am confined to bed

2. **Self-Care**

- a. I have no problems with self-care
- b. I have some problems washing or dressing myself
- c. I am unable to wash or dress myself

3. **Usual Activities** (*e.g. work, study, housework, family or leisure activities*)

- a. I have no problems with performing my usual activities
- b. I have some problems with performing my usual activities
- c. I am unable to perform my usual activities

4. **Pain/Discomfort**

- a. I have no pain or discomfort
- b. I have moderate pain or discomfort
- c. I have extreme pain or discomfort

[figure not shown]
5. **Anxiety/Depression**

- a. I am not anxious or depressed
- b. I am moderately anxious or depressed
- c. I am extremely anxious or depressed

To help people say how good or bad a health state is, we have drawn a scale (rather like a thermometer) on which the best state you can imagine is marked 100 and the worst state you can imagine is marked 0.

We would like you to indicate on this scale how good or bad your own health is today, in your opinion. Please do this by drawing a line from the box below to whichever point on the scale indicates how good or bad your health state is today.

**Your own
health state
today**

Please check to make sure you have answered all questions.

Please fill in your initials to indicate that you have completed this questionnaire: _____
Today's date (Year, Month, Day): _____

Thank you.

